Protocol

Title

Cost-effectiveness of models of care for young people with eating disorders (CostED)

Research team

Principal investigator [name], King's College London Trial managers [name], King's College London [name], Queen's University Belfast **Co-investigators** [name], King's College London [name], Great Ormond Street Hospital [name], University of Liverpool [name], King's College London [name], Beat (Beating Eating Disorders) [name], Queen's University, Belfast [name], Our Lady's Children's Hospital, Dublin [name], University of Exeter [name], South London and Maudsley NHS Trust [name], Abergele Hospital [name], South London and Maudsley NHS Trust

Summary of amendments

Amendment	Reason	Date	Version
CGAS added as an outcome measure	More commonly used in clinics	01/11/13	v1.1
Follow-up reduced from 9 and 18 months to 6 and 12 months	Delays in approvals and concerns from CAPSS about burden on clinicians and likelihood of remaining in contact	07/03/14	v1.1
Start and end dates corrected in the Plan of Investigation and Timetable section	Incorrect dates entered in previous version	06/01/15	v1.2

Background

Anorexia nervosa (AN) is a severe and enduring mental health problem with an annual incidence in the most vulnerable group (adolescent girls aged 15-19 years) of between 110-135 per 100,000.[1,2] AN is commonly associated with severe physical, psychological and social impairments, high levels of mortality[3] and a significant cost burden.[4,5] Although the majority of adolescents with AN eventually recover, the illness is often protracted, with a mean duration of 5-6 years.[6] Because AN is potentially life threatening, a significant proportion of young people with AN will be treated as inpatients in hospital. Nationally 35% or more adolescents with AN [7] and over 50% of children with AN [8] are admitted to hospital at some point. The number of admissions to hospital for eating disorders in under 14s rose consistently over the decade between 2000 and 2010,[9] and children under 18 now account for more than one in three hospital stays for eating disorders. Although some admissions (mainly on paediatric wards) are brief, many are as long as 6-12 months and in some cases longer. Hospital admission is disruptive to school, family and social life and relapse rates for inpatient treatment are high (25-30% after first admission and 50-75% after subsequent admission),[6,10] with evidence that clinical outcomes may be worse even when severity is accounted for.[11] In contrast those who have responded well to outpatient family therapy have low relapse rates of 5-10%.[12-14]

There are two main community-based care pathways for young people with AN. The first and most common is from primary care to a generic, local child and adolescent mental health service (CAMHS) that will have varying levels of expertise in eating disorders and a variable mix of individual or family-based treatments. In some cases, this may include a specific eating disorders "mini-team". The second referral route is from primary care directly to a specialist outpatient child and adolescent eating disorder service (CAEDS). These are tertiary level dedicated, multidisciplinary services that cover a larger geographical area than a single CAMH service and have been reported to reduce rates of admission to hospital by as much as 60-80%.[15] Although these have been growing in number in recent years, they are still relatively rare in the British Isles.

There is limited service level research in eating disorders comparing the relative benefits of different care pathways for young people with AN. One study, the Treatment Outcome for Child and Adolescent Anorexia Nervosa (TOuCAN) trial, which compared brief treatment in a specialist service with treatment as usual in CAMHS and inpatient treatment, found no differences in clinical outcomes [16] but a significant difference in cost favouring the specialist service.[17] All groups made considerable progress at one year, with further improvement by two years, though full recovery rates were low. Although neither inpatient nor specialist outpatient treatment demonstrated statistically significant advantages over general CAMHS care, initial inpatient treatment predicted poor outcomes and did not provide advantages over outpatient management. Importantly, in those cases where outpatient treatment had failed and the young person was transferred to inpatient facilities, the outcome was poor. On the basis of the cost-effectiveness analysis, the study concluded that specialist outpatient treatment had the highest probability of being the most costeffective treatment strategy.[17] A London based study [18] compared areas with CAED services accepting direct referrals from GPs with areas with no such services, where treatment would normally be offered in generic CAMHS with further referral (to inpatient or specialist outpatient) if deemed necessary. The study found three key differences between these care pathways. First, case identification of adolescent AN in specialist areas was high, approximately at a level predicted by epidemiological studies, suggesting that the services were largely meeting the actual need in the community. In non-specialist areas, rates of referrals were more than 50% lower. Second, there were significant differences in the rates of admission to hospital between those whose treatment started in a specialist service (16%) and those first treated in generic CAMHS (40%). Third, there were differences in the continuity of care. For a young person whose treatment was initiated in a specialist outpatient service, 83% received all their care from the same team. By contrast, those assessed initially in generic CAMHS, continued treatment in the service without further referral in only 20% of cases. This lack of continuity of care was identified as a key problem by parents who took part in a qualitative exploration of experience of care.[19] Although the results in boroughs with specialist eating disorders "mini-teams" were variable, in general they were more comparable to specialist CAED teams than to generic non-specialist CAMHS.

Despite these findings, many parts of the British Isles have little or no specialist eating disorder provision for young people. The available evidence suggests that, if the above findings are generalized, investing in the development of such services could have significant implications for the NHS, with the potential to improve health outcomes through reductions in relapse rates, to reduce costs through reductions in hospital admission, and to improve the quality of life of young people. However, service commissioners are unlikely to support increased investment in specialist services at a time when disinvestment is more pressing. Clear evidence of the savings to be made from investment is therefore needed, alongside evidence that patient and family outcomes will be enhanced or at least no worse than the current situation. The proposed work aims to provide such evidence through the exploration of the cost and cost-effectiveness of existing community-based models of service provision in the British Isles.

Aims and objectives

This study aims to evaluate the cost and cost-effectiveness of existing communitybased models of service provision for child and adolescent anorexia nervosa (AN) and to model the impact of potential changes to the provision of specialist NHS services using decision analytic modelling techniques.

The objectives of the study are:

- 1) To identify all new community-based incident cases of AN in young people aged 8-18 in the British Isles over a 12-month period using a psychiatric surveillance system;
- 2) To classify the model of community-based care provided for each case identified at baseline and map models of care across the British Isles using a brief questionnaire to reporting clinicians;
- 3) To calculate the relative cost of all incident cases of child and adolescent AN in England, Wales and Northern Ireland and determine the cost and cost-

effectiveness of different models of care provision at 6-month and 12-month follow-up through questionnaires to reporting clinicians;

4) To explore the impact on cost and cost-effectiveness of potential changes to the provision of specialist services in England, Wales and Northern Ireland using decision analytic modelling techniques.

The hypotheses of the study are that:

- Assessment and treatment by highly specialist or tertiary specialist community-based eating disorder services for child and adolescent AN in England, Wales and Northern Ireland will be less costly to the health service over 12-months than assessment and treatment by or referral via generic (nonspecialist) child and adolescent mental health services (CAMHS) or eating disorder teams located within generic community CAMHS.
- 2) Assessment and treatment by highly specialist or tertiary specialist community-based eating disorder services for child and adolescent AN in England, Wales and Northern Ireland will be more cost-effective from the health service perspective over 12-months than assessment and treatment by or referral via generic (non-specialist) CAMHS or eating disorder teams located within generic CAMHS.
- 3) Increasing the availability of highly specialist or tertiary specialist communitybased eating disorder services for child and adolescent AN in England, Wales and Northern Ireland will be cost-saving to the health service over the medium to long-term.

Methods

Study design

The study will involve the development of a decision analytic model to explore the impact of potential changes to the configuration of community-based services for child and adolescent AN on relative cost and cost-effectiveness.

Sampling

The model will be populated with data on all incident cases of child and adolescent AN in England, Wales and Northern Ireland, collected over a 12-month period via a naturalistic surveillance study using the Child and Adolescent Psychiatric Surveillance System (CAPSS).[20] CAPSS is a system designed to ascertain cases of rare childhood mental health conditions which relies on non-consent to maximise accuracy of incidence data. CAPSS aims to facilitate epidemiological surveillance and research into uncommon child and adolescent mental health conditions, increase awareness within the medical profession and public alike of the less common psychiatric disorders that afflict children and allow psychiatrists to participate in surveillance of such conditions.

CAPSS uses a report card, known as the yellow card, which contains a list of conditions being surveyed. The yellow card, along with reporting instructions and protocols for new studies, is sent every month to a mailing list of all hospital, university and community paediatric consultant psychiatrists who are members of the Royal College of Psychiatrist or respective Irish colleges, currently totalling 1000 respondents. The aim is to involve every senior doctor who is likely to have clinical

responsibility for children with rare conditions. The reporting clinicians are sent yellow cards from the CAPSS office and asked to check boxes against any of the reportable conditions they have seen in the preceding month, or to check a "nil return" box if none have been seen, and return the card to the CAPSS office. A tear-off slip is provided with the card for the psychiatrists to keep a convenient record of patients reported. "Positive" returns are identified by the CAPSS administrator and then notified to the appropriate research investigator, who then contacts the reporting clinician directly to request completion of a brief data collection form.

CAPSS uses an inclusive system which covers the whole of the UK and Eire. Whilst the focus of the NIHR HS&DR is on England and Wales, the collection of CAPSS data from specific regions or countries within the British Isles is not encouraged and open to error. Instead, baseline data from incident cases will be collected from the whole of the British Isles (Objective 1) and used to support the classification of models of community-based care and the mapping of models of community-based service provision (Objective 2). However, follow-up data to calculate the cost and cost-effectiveness of different models of community-based service provision (Objective 3) and to populate the decision analytic model (Objective 4) will be collected only from those cases reported in England and Wales, plus Northern Ireland which is funded separately. The option to collect follow-up data from the rest of the British Isles will be retained as a contingency plan should recruitment be lower than expected.

Setting/context

The proposed work is focused on community-based health services for child and adolescent AN. However, a substantial proportion of cases are admitted to hospital at some point during the course of their illness so the setting will cover both community-based and hospital-based secondary and tertiary mental health services.

Inclusion and exclusion criteria

Children and adolescents aged 8-18, in contact with community-based mental health services for a first episode of AN, according to DSM-V criteria.[21] Cases currently in secondary or tertiary inpatient facilities will be included in the incidence and service mapping objectives (objectives 1 and 2) but excluded from the follow-up study (objectives 3 and 4), although these cases will be eligible for inclusion if they are subsequently notified after discharge to community services. We will also exclude cases of young people whose clinician-reported data is insufficient to assess eligibility or duplicate cases, that have been notified more than once by the same or different clinicians.

Sample size

For the survey (Phase 1 of the study), the concept of a 'sample size' (which allows inferences to be made about the population as a whole) is not helpful since we are aiming to collect population level data. The aim is to identify *all* incident cases of anorexia nervosa in the UK and Eire over a 12-month period, in order to come to conclusions in relation to the population, rather than making inferences about the population from a smaller sample.

Phase 2 of the study involves decision analytic modelling to support real-world decisions relating to the configuration of community-based services for child and

adolescent AN. Decision-analytic modelling is a systematic approach to decision making which aims to inform decisions under conditions of uncertainty. Issues of statistical significance are unhelpful in this context. Instead, a decision-making approach is advocated which attempts to make the most of the data available by focusing less on issues of statistical significance and more on the probability of one intervention or service configuration being more cost-effective than another, given the data available, rather than undertaking what is likely, given low prevalence rates in AN, to be a prohibitively large RCT.[22]. The TOuCAN study, for example, was a large multi-centre, population based study including the majority of cases in the entire North West region of the UK.[16,17] Yet despite large differences in cost between the three included groups, these differences were not found to be statistically significant, suggesting inadequate power and thus an inadequate sample size. Any attempts to increase the sample size would be extremely difficult and would need to involve additional regions, not just additional centres.

From a statistical point of view, commentators stress that the absence of evidence is not evidence of absence.[23] Similarly, from a decision-making point of view, the perversity of ruling out an intervention which has the highest probability of being cost-effective has been highlighted as a limitation of conventional hypothesis testing.[24,25] Although observed differences may indeed be the result of chance, a decision still has to be made and these authors argue that it is better to use the available evidence than to dismiss it on the basis of an arbitrary decision rule. It should then be left to the decision-maker to assess the quality of the available evidence and decide whether or not there is a need for further information. In the meantime, the decision-maker would do better to select the intervention with the highest probability of being cost-effective, than to simply maintain the status quo. This is the approach taken in this proposal. The following provides estimates for expected baseline and follow-up rates.

Primary care estimates

Primary care based data for anorexia nervosa collected in the UK between 1994 and 2000 reported incidence rates for children and adolescents aged between 10 to 19 of 34.6 per 100,000 for females and 2.3 per 100,000 for males.[26] For children aged 0 to 9, the incidence rate was zero. More recent UK estimates for young people aged 10 to 19 indicate a small increase in incidence rates to 37.1 per 100,000 for females and 3.2 per 100,000 for males.[27] We applied these more recent estimates, broken down by age and gender where possible, to population data for the UK and the Republic of Ireland [28,29] for young people aged between 10 and 18 (the maximum age included in the proposed study). Estimates for younger children were only available from the earlier study.[26] The results are reported in Table 1. These incidence rates suggest an estimated number of new cases of AN in primary care in the British Isles over a 12-month period of 1329 (approximately 1215 females and 115 males).

			Number					
Age	Gender	Incidence	Population by age		of cases		Total	Source
			UK	RoI	UK	RoI		
8-9	Both	0.00	1,333,900	126,416	0	0	0	[26]
10-14	Female	24.00	1,741,600	147,415	418	35	453	[27]
10-14	Male	2.50	1,825,400	155,076	46	4	50	[27]
15-18	Female	47.50	1,494,000	110,237	710	52	762	[27]
15-18	Male	3.80	1,581,800	115,700	60	4	65	[27]
Total							1329	[27]

Table 1: Incidence estimates from primary care data

Secondary care estimates

Data from secondary care studies are more limited. Data from a London care pathways study [18] suggests an incidence rate of 54.6 for young women aged between 13 and 18, including anorexia nervosa and EDNOS-AN, a proportion of which is now classified as anorexia nervosa under DSM-V. Data for young men was not reported as the numbers were so small. For the younger ages, data is available from a British national surveillance study carried out in 2005/2006 using the CAPSS system.[8] Application of these rates to UK and Republic of Ireland population data [28,29] is reported in Table 2, broken down by age and gender where data allowed. For males aged 13 to 18, primary care rates have been used due to the lack of secondary care data for this group.[27] These incidence rates suggest an estimated number of new cases of anorexia nervosa in the British Isles over a 12-month period of 1435, slightly higher than the primary care estimate, above. However, given that the majority of these cases were estimated using London data,[18] we have adjusted these figures downwards to take into account the fact that the incidence rates in London may be higher than the British Isles more broadly as a result of the greater concentration of specialist eating disorder services in London. We have reduced the London incidence rate by 10% and by 20%, as shown in Table 2.

		Number of					
Gender	Incidence	Population		cases		Total	Source
		UK	RoI	UK	RoI		
Total	0.00	666,300	63,581	0	0	0	[8]
Total	0.72	667,600	62,386	5	0	5	[8]
Total	1.42	683,300	61,181	10	1	11	[8]
Total	1.69	703,100	60,587	12	1	13	[8]
Total	3.63	715,500	60,926	26	2	28	[8]
Female	54.60	2,208,700	168,213	1206	92	1298	[18]
Male	2.50	750,300	61,018	19	2	20	[27]
Male	3.80	1,581,800	115,700	60	4	65	[27]
						1440	
London incidence rate reduced by 10%						1310	
London incidence rate reduced by 20% 1180							
	Total Total Total Total Total Female Male Male incidence	Total0.00Total0.72Total1.42Total1.69Total3.63Female54.60Male2.50Male3.80	UK Total 0.00 666,300 Total 0.72 667,600 Total 1.42 683,300 Total 1.69 703,100 Total 3.63 715,500 Female 54.60 2,208,700 Male 2.50 750,300 Male 3.80 1,581,800	UKRoITotal0.00666,30063,581Total0.72667,60062,386Total1.42683,30061,181Total1.69703,10060,587Total3.63715,50060,926Female54.602,208,700168,213Male2.50750,30061,018Male3.801,581,800115,700	Gender Incidence Population case UK RoI UK Total 0.00 666,300 63,581 0 Total 0.72 667,600 62,386 5 Total 1.42 683,300 61,181 10 Total 1.69 703,100 60,587 12 Total 3.63 715,500 60,926 26 Female 54.60 2,208,700 168,213 1206 Male 2.50 750,300 61,018 19 Male 3.80 1,581,800 115,700 60	Gender Incidence Population cases UK RoI UK RoI Total 0.00 666,300 63,581 0 0 Total 0.72 667,600 62,386 5 0 Total 1.42 683,300 61,181 10 1 Total 1.69 703,100 60,587 12 1 Total 3.63 715,500 60,926 26 2 Female 54.60 2,208,700 168,213 1206 92 Male 2.50 750,300 61,018 19 2 Male 3.80 1,581,800 115,700 60 4	$\begin{array}{c c c c c c c c c c c c c c c c c c c $

Table 2: Incidence estimates from secondary-care data

Approach taken

The estimates presented suggest a total population of new cases of AN in secondary care of between 1,200 and 1,400 per annum. Using data from the previous British national surveillance study,[8] we have calculated the following expected rates of case

notification at baseline and response rates at follow-up, dependent on whether new cases are the higher or lower of these estimates:

Tuble 5. Expected futes of cuse notification and follow up over 12 months							
Lower	Higher						
estimate	estimate						
1200	1400						
900	1050						
765	893						
880	1026						
765	893						
650	759						
520	607						
478	558						
407	474						
305	356						
	Lower estimate 1200 900 765 880 765 650 520 478 407						

Table 3: Expected rates of case notification and follow-up over 12-months

¹ We assumed 15% for duplicates; 31% duplicates were reported in the British national surveillance study however this included both paediatricians and psychiatrists, thus increasing the likelihood of duplicate notifications

² We assumed 15% exclusion due to insufficient data as reported in the national surveillance study

³ We assumed 20% exclusion due to reporting errors -29% reported in national surveillance study however we plan to contact clinicians by telephone to minimise this so lower rate applied (n=864)

Limitations of the approach

There is limited evidence of incidence rates of AN in secondary care settings – the setting of interest to the current study. Most evidence uses data from primary care or, in the case of the British National Surveillance Study which based estimates on CAPSS notifications,[8] focuses on younger children than we plan to include (under 13s). The estimates presented here are primarily based on one London study,[18] which may not accurately reflect the rest of the British Isles. Our adjustments for the likely over-estimate within a London sample are not evidence-based and thus may not be accurate.

In addition, the London study includes both AN and EDNOS-AN, according to DSM-IV diagnostic criteria. However new DSM-V definitions of anorexia nervosa include a large proportion of what used to be known as EDNOS-AN.[21] The size of this group is currently unknown. We have therefore assumed it to be 100% (i.e. all EDNOS-AN defined by DSM-IV is classified as anorexia nervosa using DSM-V), so the expected number of notifications presented here may be an over-estimate. The figures presented should therefore be considered the maximum expected.

Baseline data – UK and Eire

Upon notification from the CAPSS system of a new case of child and adolescent AN, the notifying clinician will be sent a brief questionnaire to confirm eligibility of the case and to support the categorisation of the model of service delivered and the geographical mapping of models of care across the British Isles. Classification will focus on the service undertaking the initial assessment. Classifications will be refined as part of the study, however we anticipate a classification system based on the following criteria:

- Tertiary specialist child and adolescent eating disorder service (CAEDS) containing a trained, multi-disciplinary team, including medical and non-medical staff, and more than one person with experience of treating eating disorders, with the necessary expertise to deliver recommended treatments for adolescents (i.e. psychological therapy, assessment of physical risk and family interventions addressing the eating disorder), and having resources required to offer routine outpatient treatment for a minimum of 25 cases per year.[30] CAED services cover larger geographical areas than a single CAMHS
- Specialist CAMHS teams based in a generic secondary care CAMHS but containing a specialist eating disorder component. These teams operate within a single CAMHS setting, have a more limited multidisciplinary input and a smaller throughput of eating disorder cases than CAEDS.
- Generic secondary (non-specialist) CAMHS services.

Following initial mapping of services we will convene an independent expert group using Delphi methodology to help specify an operational definition for specialist teams in order to differentiate them clearly from non-specialist CAMHS teams.

Follow-up data - England, Wales and Northern Ireland

Six months and 12-months after notification, the notifying clinician and/or the notifying service will be re-contacted by phone to collect anonymised information on the following:

Health service use

Health service use since notification, including frequency and length of inpatient admissions and number of hospital or community based outpatient contacts. Whilst this is a narrow cost perspective, excluding broader health, social and education services, two year total costs in the TOuCAN study which took a societal perspective, were found to be heavily dominated by hospital costs and CAMHS community outpatient costs.[17] Together, inpatient and outpatient costs were found to account for over 90% of total two-year costs.[31] Thus, a narrow perspective will minimise respondent burden, and allow us to take advantage of surveillance methodology which traditionally does not involve direct patient contact, whilst still providing evidence of the key costs in this population.

Outcomes

Whilst costs are the primary variable of interest in the proposed work, measures of effectiveness will also be collected to confirm previous evidence from treatment trials to suggest specialist treatments are at least as effective as standard care and to provide up to date evidence for inclusion in the economic modelling component of the study. Outcome data will be collected from treating clinicians and assessed in terms of key indicators, including age adjusted percentage median body mass index (BMI), Health of the Nation Outcome Score for Children and Adolescents (HoNOSCA), a routine outcome measurement tool that assesses behaviours, impairments, symptoms, and social functioning of children and adolescents with mental health problems,[32] outcome category according to the Morgan and Russell criteria, a widely used measure of outcome for anorexia nervosa,[33] and the Children's Global Assessment Scale (CGAS), used to rate the emotional and behavioural functioning of children and

adolescents in the family, school, and social context, and designed for use in telephone interviews with treating clinicians.[34]

Analysis

Incidence of child and adolescent AN

Assessment of the current incidence of AN in children and adolescents aged 8 to 18 in the British Isles will be primarily descriptive. Where duplicates are reported, data will be used from the most complete data-set, or the data-set received closest to the reporting date. Incidence will be calculated as number of cases as a proportion of the total number of children of that age in the population (UK plus ROI) expressed as per 100,000 population. Total population data for children and adolescents aged 8–18 will be obtained from the Office of National Statistics (UK) and the Central Statistics Office (Ireland).[28,29] The incidence rates calculated will update evidence from previous studies, now over ten years old,[26] and fill the gap in the literature relating to older young people, given more recent research (2005 to 2006) focused only on early onset eating disorders (<13 years of age).[8]

Cost of child and adolescent AN

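### Incidence is defined with no allowance for incomplete ascertainment, although Table 3 appears to expect only about 54–64% of new cases to remain as usable unique cases

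*Protocol*

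**What the plan says.** In the Protocol's Analysis section, under incidence of child and adolescent AN, the rule is: "Incidence will be calculated as number of cases as a proportion of the total number of children of that age in the population". The population is the UK plus the Republic of Ireland, ages 8–18, and the rate is per 100,000. The section calls the assessment mainly descriptive, gives a rule for choosing between duplicate reports, and says the new rates will bring older published figures up to date. It mentions no adjustment for non-reporting, missing questionnaires or exclusions.

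Under Sample size, the Protocol sets aside the idea of a sample size for the survey "since we are aiming to collect population level data".

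Under Approach taken, it puts forward "a total population of new cases of AN in secondary care of between 1,200 and 1,400 per annum". Table 3 then sets out expected "notification at baseline and response rates at follow-up, dependent on whether new cases are the higher or lower of these estimates". The lower column reads "Lower estimate 1200 900 765 880 765 650 520 478 407", and the higher column runs from 1400 through 893 and 759 to 607 at the corresponding steps. Three footnotes survive: "We assumed 15% for duplicates"; "We assumed 15% exclusion due to insufficient data as reported in the national surveillance study"; "We assumed 20% exclusion due to reporting errors". The inclusion and exclusion criteria confirm that cases with data too thin to judge eligibility are left out.

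**The concern.** Numerator and denominator do not cover the same children. The denominator includes those under the care of clinicians who never return a card or questionnaire, and those whose returned data could not be used. The numerator can only include cases that were notified and confirmed. The Protocol itself forecasts a sizeable gap between the two, and the incidence rule does not carry that gap forward.

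Estimating incidence is Objective 1, and the result is meant to stand next to earlier rates. Table 1 applies primary-care rates to the same population and arrives at 1,329 cases. An uncorrected surveillance rate well below that level could be read as a decline when under-capture alone would produce it.

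**Working it through.** **Inputs.** New cases per year: 1,200 (lower) and 1,400 (higher), from Approach taken. Later counts: Table 3. Population aged 8–18: Table 1.

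**Reproducing Table 3.** The lower column follows from a chain of multipliers:

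- 1200 × 0.75 = 900
- 900 × 0.85 = 765
- 765 × 1.15 = 880 (duplicates added)
- 880 ÷ 1.15 = 765 (duplicates removed, so no net effect on unique cases)
- 765 × 0.85 = 650 (insufficient data)
- 650 × 0.80 = 520 (reporting errors)

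The same factors from 1400 give 1050, 893, 1026, 893, 759 and 607, as printed. The duplicate, insufficient-data and reporting-error steps match the footnotes. The 0.75 and first 0.85 factors are read off the counts. Their labels are not available, and taking them as non-capture is an inference.

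**Proportion remaining.**

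- Before exclusions: 765/1200 = 63.8%; 893/1400 = 63.8%
- After insufficient data: 650/1200 = 54.2%; 759/1400 = 54.2%
- After reporting errors: 520/1200 = 43.3%; 607/1400 = 43.4%

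**Denominator.**

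- UK: 1,333,900 + 1,741,600 + 1,825,400 + 1,494,000 + 1,581,800 = 7,976,700
- Republic of Ireland: 126,416 + 147,415 + 155,076 + 110,237 + 115,700 = 654,844
- Total: 8,631,544

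**Rates per 100,000** (count ÷ 8,631,544 × 100,000):

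| Basis | Lower | Higher |
|---|---|---|
| Plan's assumed total (1200; 1400) | 13.9 | 16.2 |
| Unique cases before exclusions (765; 893) | 8.9 | 10.3 |
| After insufficient data (650; 759) | 7.5 | 8.8 |

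**Shortfall.** 1 − 0.638 = 36% and 1 − 0.542 = 46%. Undoing it would mean multiplying the crude rate by 1/0.638 = 1.57 or 1/0.542 = 1.85.

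**Comparison with the older rates.** The 1,329 cases of Table 1 over the same population give 15.4 per 100,000.

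**Sampling error for scale.** With 650 cases, a Poisson 95% interval is roughly ±1.96/√650 = ±7.7%. An interval around the crude rate alone would therefore not cover a shortfall of this size.

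**The case against.** The strongest reply is that a crude rate over the resident population is a legitimate descriptive figure. Non-response adjustment and intervals are often left to a statistical analysis plan, which is not shown here. That stands for the detail of any adjustment, and a later document may supply it. It does not remove the mismatch within the Protocol, which states the formula, calls the result incidence without qualification, intends it to update earlier rates, and forecasts the loss itself.

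Second, Table 3 is a feasibility forecast, and the starting totals are described as upper limits that rest partly on London adjustments without an evidence base. Actual capture will be known only from the data. This is correct, but the proportional shortfall depends on the loss rates and not on the starting total.

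Third, some stronger readings are tempting and should be resisted:

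- A reader might take the 520 and 607 rows as showing 43% capture, a 57% bias and a published rate of less than half the truth. The last step removes reporting errors. If these are mistaken notifications, no true case is lost, so the documents do not establish the 43% figure.
- A reader might infer that no statement of uncertainty is planned. The Sample size section sets aside a sample-size calculation because all cases are sought. It does not say intervals will be omitted.
- A reader might foresee harm to regional planning. The Protocol specifies no regional incidence analysis.

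Finally, costs are the main variable of interest and none of the three hypotheses depends on incidence. That limits the reach of the point to Objective 1.

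**Conclusion.** The point holds in a limited form. The stated rule makes no allowance for incomplete ascertainment, while Table 3 appears to expect about 54–64% of new cases to remain as unique cases after non-capture and the insufficient-data exclusion. On those planning rates the crude figure would be about 7.5–10.3 per 100,000 against 13.9–16.2, which is 36–46% too low.

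This rests on three assumptions: that the two unlabelled steps (0.75 and 0.85) represent true cases not captured, that the planning loss rates are borne out, and, for the 46% end, that cases with insufficient data are as likely to be true cases as the rest. The arithmetic itself is secure. The cost hypotheses are unaffected; what is at risk is the interpretation of the Objective 1 rate against earlier figures.

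**What to change.** 1. Keep the stated ratio, but call it observed (minimum) incidence.
2. Report beside it the proportion of cards returned, the proportion of questionnaires returned, and the number of notifications excluded for insufficient data.
3. Add an ascertainment-adjusted estimate. Apply the eligible fraction seen among assessable notifications, after removing duplicates, to those with no questionnaire or insufficient data. This does not count known reporting errors as lost cases.
4. Treat card non-return as a sensitivity range and not as a fixed divisor. The plan expects 15% duplicates, so one case may have more than one reporter, and a missing card need not mean a missing case. Dividing by the card-return proportion could over-correct. Avoid making region-specific adjustment the main analysis, since the Sampling section warns that collecting surveillance data by region is prone to error.
5. Give 95% intervals for both rates.

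The cost is mainly wording and a short additional analysis. Clinicians are asked to return a card even when they have seen no case, so card-return proportions should be obtainable, although the Protocol does not say how they are recorded. The downside is that the adjusted rate assumes unreturned cases resemble returned ones and that non-returning clinicians see similar caseloads. Both assumptions should be stated with the result.
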